# Preparation of Rituximab or Ruxience for Subsequent Intravenous Infusions

- 1. Using aseptic technique, withdraw the necessary amount of rituximab or Ruxience and dilute to a final concentration of 1 to 4 mg/mL into an infusion bag containing either 0.9% Sodium Chloride, USP, or 5% Dextrose in Water, USP. It is recommended that a dilution of 2 mg/mL be used for ease in calculating dose. Gently invert the bag to mix the solution. Discard any unused portion left in the vial. Parenteral drug products should be inspected visually for particulate matter and discoloration prior to administration.
- 2. DO NOT ADMINISTER AS AN INTRAVENOUS PUSH OR BOLUS. Rituximab or Ruxience can be diluted with 5% dextrose or normal saline. In general they should not be infused with other fluids or medications, but nurses may consult with a pharmacist to check for y-site compatibility with other medications if needed.

3. If the participant tolerated the first infusion well, subsequent study drug infusions can be administered at an initial rate of 100 mg/hr and increased by 100 mg/hr increments at 30-minute intervals to a maximum of 400 mg/hr as tolerated. Such an infusion schedule is listed below. If the participant did not tolerate the first infusion well, the above guidelines for the first infusion should be followed for subsequent infusions.

Time (Minutes)	Infusion Rate (mg/h)	Dose in 30 minutes (mg)	Cumulative Dose (mg)
0-30	100	50	50
31-60	200	100	150
61-90	300	150	300
91-120	400	200	500
121-150	400	200	700
151-180	400	200	900
181-195*	400	200	1000

Should complete at 195 minutes (3h 15 min) to complete a 1000mg total dose

- 4. Infusion and hypersensitivity reactions may occur. Premedication consisting of acetaminophen and diphenhydramine will be required before each infusion of rituximab or Ruxience. Premedication may attenuate infusion reactions. Since transient hypotension may occur during rituximab or Ruxience infusion, consideration should be given to withholding antihypertensive medications 12 hours before rituximab or Ruxience infusion.
- 5. If a hypersensitivity (non-IgE-mediated) or an infusion reaction develops, the infusion rate should be reduced to half that rate, i.e. from 100 mg/h to 50 mg/h. Participants who experience a moderate to severe infusion related reaction (fever, chills, or hypotension) should have their infusion interrupted immediately and should receive aggressive symptomatic treatment. The infusion should not be restarted before all the symptoms have disappeared and then the infusion can continue at one-half the previous rate.
- 6. After the end of infusion, the intravenous line should remain in situ for at least 1 hour in order to be able to administer drugs intravenously if necessary. If there are no adverse events during this period of time, the intravenous line may be removed.

Version Date: 04/16/2025

# 16.3 APPENDIX C: MOXETUMOMAB PASUDOTOX-TDFK (LUMOXITITM) PREPARATION AND ADMINISTRATION

# **How Supplied**

- LUMOXITI and IV Solution Stabilizer are packaged separately.
- Prior to preparation, LUMOXITI and IV Solution Stabilizer should be stored at 2°C to 8°C (36°F to 46°F) in original cartons to protect from light.

## LUMOXITI (moxetumomab pasudotox-tdfk)

- Each single-dose vial supplies LUMOXITI 1 mg/vial (moxetumomab pasudotox-tdfk) for injection as a lyophilized cake or powder for reconstitution and dilution prior to intravenous infusion.
- Multiple vials of LUMOXITI may be required to administer a single dose (See Step 1: Calculate Dose on next page).
- Reconstitute LUMOXITI vials with Sterile Water for Injection, USP only (not supplied).

## **Solution Stabilizer**

- Each single-dose vial contains 1 mL IV Solution Stabilizer.
- Only one vial of IV Solution Stabilizer is needed per administration of LUMOXITI, regardless of the number of vials of LUMOXITI used to prepare the infusion.
- Do not use IV Solution Stabilizer to reconstitute LUMOXITI.
- Do not flush IV lines with IV Solution Stabilizer.

# **Storage and Handling of Reconstituted and Diluted LUMOXITI**

Table 1. Storage Times and	d Conditions for Reconstituted ar	nd Diluted LUMOXITI Solution
Reconstituted Solution	Diluted LUMOXITI Solution in	n Infusion Bag
	After Dilution	Administration
LUMOXITI does not contain bacteriostatic preservatives.  Use reconstituted solution immediately.  DO NOT STORE reconstituted LUMOXITI vials.	immediately or after storage at room temperature (20°C to 25°C; 68°F to 77°F) for up to 4 hours or store refrigerated at 2°C to 8°C (36°F to 46°F) for up to 24 hours.  PROTECT FROM LIGHT. DO NOT FREEZE.	If the diluted solution is refrigerated (2°C to 8°C; 36°F to 46°F), allow it to equilibrate at room temperature (20°C to 25°C; 68°F to 77°F) for no more than 4 hours prior to administration.  Administer diluted solution within 24 hours of reconstitution as a 30-minute infusion.  PROTECT FROM LIGHT.

- Calculate the dose (mg) and the number of LUMOXITI vials (1 mg/vial) to be reconstituted. The final concentration of the reconstituted LUMOXITI solution is 1 mg/mL.
- Individualize dosing based on the participant's **actual body weight** prior to the first dose of the first treatment cycle.
- A change in dose should only be made between cycles when a change in weight of greater than 10% is observed from the weight used to calculate the first dose of the first treatment cycle. No change in dose should be made during a particular cycle.
- **Do not** round down the dose for partial vials.

### **Step 2: Gather Supplies**

- LUMOXITI 1 mg/vial (number of vials to be reconstituted are based on Step 1)
- 1 vial of IV Solution Stabilizer (packaged separately)
- Alcohol swabs
- 1 infusion bag containing 50 mL or 100 mL 0.9% Sodium Chloride Injection, USP
- Sterile Water for Injection, USP
- Syringes and needles

## **Step 3: Reconstitution**

- Reconstitute each LUMOXITI vial with 1.1 mL Sterile Water for Injection, USP using aseptic technique.
- Direct the Sterile Water for Injection, USP slowly **along the walls** of the LUMOXITI vial and not directly at the lyophilized cake or powder.
- **Do not** reconstitute LUMOXITI vials with the IV Solution Stabilizer.
- **Gently** swirl the vial until completely dissolved. Invert the vial to ensure all cake or powder in the vial is dissolved. **Do not shake.**
- Visually inspect that the reconstituted solution is clear to slightly opalescent, colorless to slightly yellow, and free from visible particles.
- **Do not** use if solution is cloudy, discolored, or contains any particles.
- The resulting 1 mg/mL solution allows a withdrawal volume of 1 mL.

Note: Use reconstituted solution immediately. Do not store reconstituted LUMOXITI vials. See Table 1 for storage times and conditions for the reconstituted solution.

## Step 4: Preparation of Infusion Bag with IV solution Stabilizer

- Obtain a 50 mL 0.9% Sodium Chloride Injection, USP infusion bag.
- Only one vial of IV Solution Stabilizer is needed per administration of LUMOXITI, regardless of the number of vials of LUMOXITI used to prepare the infusion.
- Add 1 mL IV Solution Stabilizer to the infusion bag containing 50 mL 0.9% Sodium Chloride Injection, USP.
- Gently invert the bag to mix the solution. **Do not shake.**

#### **Step 5: Dilution**

- Slowly withdraw the required volume of reconstituted LUMOXITI solution needed from each vial, per the calculated dose based on the participant's actual body weight (kg).
- Inject LUMOXITI into the infusion bag containing 50 mL 0.9% Sodium Chloride Injection, USP and 1 mL IV Solution Stabilizer.
- Gently invert the bag to mix the solution. Do not shake.

- Discard any partially used or empty vials of LUMOXITI and IV Solution Stabilizer.
- See **Table 1** for storage times and conditions for the diluted solution.

## **Step 6: Intravenous Hydration and Pre-Infusion Medications:**

- Administer intravenous hydration and premedication to the participant.
- Intravenously administer 1 L of isotonic solution (e.g. 5% Dextrose Injection, USP and 0.45% or 0.9% Sodium Chloride Injection, USP) over 2 to 4 hours before each LUMOXITI infusion. Administer 0.5 L to participants under 50 kg. On day 1 of cycles 2-8, prehydration may be started during the rituximab infusion provided it is completed no earlier than 2 hours prior to the LUMOXITI infusion.
- Premedicate 30 to 90 minutes prior to each LUMOXITI infusion with anantihistamine (e.g. diphenhydramine), acetaminophen, and a histamine-2 receptor antagonist (e.g. famotidine, or cimetidine), with the exception of day 1 of cycles 2-8, when premedications are to be given prior to Rituxan.

## **Step 7: Administration**

- Infuse the diluted LUMOXITI solution intravenously using early call back/reverse flow method over 30 +/- 5 minutes.
- **Do not** mix LUMOXITI, or administer as an infusion with other medicinal products.
- After the infusion, flush the intravenous administration line with of 0.9% Sodium Chloride Injection, USP at the same rate as the infusion. This ensures that the full LUMOXITI dose is delivered.

# **Step 8: Post-infusion Medications**

- Administer post-infusion medications.
- Intravenously administer 1 L of isotonic solution (e.g. 5% Dextrose Injection, USP and 0.45% or 0.9% Sodium Chloride Injection, USP) over 2 to 4 hours after each LUMOXITI infusion. Administer 0.5 L to participants under 50 kg.
- Consider oral antihistamines and acetaminophen for up to 24 hours following LUMOXITI infusions.
- Consider oral corticosteroid (e.g. 4 mg dexamethasone) to manage nausea and vomiting.
- Maintain adequate oral fluid intake.
- Advise all participants to adequately hydrate with up to 6 L (twelve 8-oz glasses) of oral fluids (e.g. water, milk, or juice) per 24 hours on Days 1 through 8 of each 28-day treatment cycle. In participants under 50 kg, up to 2 L (eight 8-oz glasses) per 24-hour period is recommended.
- Consider low-dose aspirin on Days 1 through 8 of each 28-day treatment cycle.

Note: This Healthcare Provider Instructions for Use has been approved by the U.S. Food and Drug Administration.

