## **Eligibility:**

- HCL or HCLv with at least 1 prior purine analog, and, for HCL participants with ≥2-years 1 month response, at least 1 other therapy.
- Need for treatment, either 1) ANC <1/nL, 2) Hgb <10g/dL, 3) Plt <100/nL, 4) symptomatic splenomegaly, or enlarging HCL mass > 2cm in short axis
- Serum creatinine < 1.5 mg/dL, or creatinine clearance  $\geq$  60 mL/min by Cockcroft-Gault equation, where creatinine clearance = (140-age)(kg weight)/(72 x Creatinine).
- No uncontrolled infection or cardiopulmonary dysfunction

Version Date: 04/16/2025

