#### • Administration:

- O Participants 1-13: Moxetumomab pasudotox-tdfk 30-40 mcg/kg intravenous (iv) over 30 min, rituximab 375 mg/m² iv, 50-400 mg/hr.
- o Participants 14-26: Moxetumomab pasudotox-tdfk 40 mcg/kg intravenous (iv) over 30 min, Ruxience 375 mg/m² iv, 50-400 mg/hr
- Rituximab or Ruxience day 1 (begin day -2 on cycle 1), Moxetumomab pasudotox-tdfk days 1, 3, and 5.
- Participants will receive up to 4 cycles past documentation of CR without MRD, maximum
   8.
- o To prevent renal toxicity and hypovolemia, participants will be encouraged to drink water gradually, approximately 1 cup/hour or 6L/day, not going >3 hours without drinking from days 1 to 8 and to keep a hydration diary to record daily fluid consumption.
- o To prevent rituximab/Ruxience toxicity, participants will receive prophylactic dexamethasone orally 0.5-2 hours before the 1st dose of rituximab/Ruxience, and before subsequent doses until rituximab/Ruxience infusion reactions are not seen. Participants will also receive diphenhydramine, famotidine and acetaminophen.
- O Dexamethasone 4 mg orally (maximum 2 doses/day) will be given as needed to treat nausea or fever associated with Moxetumomab pasudotox-tdfk, which might prevent adequate water intake

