#### 3.1.3 Dose Escalation

The original plan was to treat up to 10 participants at the 40 mcg/kg dose level, up to 16 total participants could have been required (including up to 10 participants at the 30 mcg/kg dose level) if there were 2 DLTs within the first 6 participants treated at the 40 mcg/kg dose. The accrual ceiling was set at 20 participants considering screen failures and/or inevaluable participants. Please refer to Section 10.2 for dose-escalation rules and below.

Initially, 3 participants were to be treated with moxetumomab pasudotox-tdfk 30 mcg/kg and rituximab 375 mg/m^2. If 0/3 had a DLT, then the next 3 participants would be treated with moxetumomab pasudotox-tdfk 40 mg/kg and rituximab 375 mg/m^2.

[figure not shown]
If 1/3 initial participants treated with 30 mcg/kg had a DLT, then 3 more would have been treated at 30 mcg/kg. If no more than 1 of the first 6 had a DLT, then 4 more participants were to have been enrolled at 30 mcg/kg provided that no more than a total of 2 of the 10 at the 30 mcg/kg level would have a DLT.

If participants were accrued to the 40mcg/kg level, if 0/3 or 1/3 had a DLT, then 3 more were to be treated using those dose levels. If no more than 1 of the first 6 had a DLT, then 4 more participants were to be enrolled provided that no more than 2 total of the 10 at the 40 mcg/kg level had a DLT with the exception of the types noted. If a 3rd participant had a DLT, accrual would end as soon as this is noted.

If 2 of the first 3 participants, or 2 of the first 6 participants, treated with moxetumomab pasudotox-tdfk 40 mcg/kg and rituximab 375 mg/m² had a DLT, then 3 additional participants were to be treated with moxetumomab pasudotox-tdfk 30 mcg/kg and rituximab 375 mg/m². If 0/3 or 1/3 of these next 3 had a DLT with these dose levels, then 4 more participants were to be enrolled at the 30 mcg/kg level provided that no more than 2 total of the 10 at the 30 mcg/kg level had a DLT. If 2 participants in the first 6 had a DLT at this level, then the trial would have ended accrual.

Furthermore, at any time in the 10 participants, if a 3rd participant had a DLT, accrual will also end as soon as that was noted.

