#### 10.2 SAMPLE SIZE DETERMINATION

- The initial sample size determination: Up to 10 participants are intended to be treated in the trial using the following plan; if a different dose of moxetumomab pasudotox-tdfk is required, up to 16 participants will be needed to be enrolled.
  - Initially, 3 participants will be treated with moxetumomab pasudotox-tdfk 30 mcg/kg and rituximab 375 mg/m^2. If 0/3 have a DLT, then the next 3 participants will be treated with moxetumomab pasudotox-tdfk 40 mg/kg and rituximab 375 mg/m^2.

If 1/3 initial participants treated with 30 mcg/kg have a DLT, then 3 more will be treated at 30 mcg/kg. If no more than 1 of the first 6 have a DLT, then 4 more participants will be enrolled at 30 mcg/kg provided that no more than a total of 2 of the 10 have a DLT with the exception

Version Date: 04/16/2025

of the types noted. The upper one-sided 90% confidence bound on 2/10 is 45.0%. if a 3rd participant has a DLT, accrual will end as soon as this is noted.

If participants are accrued to the 40mcg/kg level, if 0/3 or 1/3 have a DLT (with the exception of the types noted), then 3 more will be treated using those dose levels. If no more than 1 of the first 6 have a DLT, then 4 more participants will be enrolled provided that no more than 2 total of the 10 have a DLT. The upper one-sided 90% confidence bound on 2/10 is 45.0%. if a 3rd participant has a DLT, accrual will end as soon as this is noted.

If 2 of the first 3 participants, or 2 of the first 6 participants, treated with moxetumomab pasudotox-tdfk 40 mcg/kg and rituximab 375 mg/m² have a DLT, then 3 additional participants will be treated with moxetumomab pasudotox-tdfk 30 mcg/kg and rituximab 375 mg/m². If 0/3 or 1/3 of these next 3 have a DLT with these dose levels, then 4 more participants will be enrolled at the 30 mcg/kg level provided that no more than 2 total of the 10 have a DLT with the exception of the types noted. If 2 participants in the first 6 have a DLT at this level, then the trial will end accrual. Furthermore, at any time in the 10 participants, if a 3rd participant has a DLT, accrual will also end as soon as this is noted. The upper one-sided 90% confidence bound on 2/10 is 45.0%.

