## 12.4.4.8 Imaging

In addition to the radiation risks discussed below, CT scans may include the risks of an allergic reaction to the contrast. Participants might experience hives, itching, headache, difficulty breathing, increased heartrate and swelling.

The risks of MR imaging are relatively small.

The US Food and Drug Administration has issued warnings that administration of gadolinium (updated September 9, 2010), the MRI contrast imaging agent used in this protocol, has been associated with development of a disease called nephrogenic systemic fibrosis (NSF). The syndrome is rare (approximately 600 cases reported worldwide as of September 2010, out of several million administrations of gadolinium), but disabling and in some cases, fatal. All cases to date have occurred in participants with severe renal disease, including participants on dialysis. NSF has been nearly eradicated secondary to careful screening of renal function and avoiding use of gadolinium in participants with eGFR <30 ml/min/1.73 BSA. Even in participants with end stage renal disease, there have been only rare occurrences of NSF because of precautions taken to use more stable contrast agents at lower doses. This protocol excludes participants with severe renal insufficiency (eGFR <30 ml/min/1.73 BSA). The FDA has issued warnings in 2017 and 2018 that some gadolinium may be retained in the brain, bone and skin although health risks of accumulation have not been reported to date. In accordance with the FDA Drug Safety Communication of 05/16/2018, the Medication Guide for gadobutrol (or other macrocyclic gadolinium contrast agent if applicable) will be made available to all participants with scans that will involve gadolinium-based contrast agent administration.

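### Hydration instructions contradict each other on glass count and for participants under 50 kg; a stated eGFR exclusion and two dose-unit entries also need reconciling

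*Combined protocol and SAP*

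**What the plan says.** **Oral fluids.** Appendix C, Step 8 instructs: "Advise all participants to adequately hydrate with up to 6 L (twelve 8-oz glasses) of oral fluids", on days 1 to 8 of each cycle. It then adds: "In participants under 50 kg, up to 2 L (eight 8-oz glasses) per 24-hour period is recommended". The Précis (Administration) asks for "approximately 1 cup/hour or 6L/day", and Section 3.2.1 repeats those amounts. The Section 3.2.3 scheme lists 6 L of water on each of days 1 to 8. None of these three places distinguishes by weight.

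**Intravenous fluids.** The Section 3.2.3 scheme lists 1 L before and 1 L after each moxetumomab infusion, for everyone. Appendix C, Steps 6 and 8, gives the same 1 L amounts but in both steps adds: "Administer 0.5 L to participants under 50 kg".

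**Renal exclusion.** Section 12.4.4.8, on gadolinium risk, states: "This protocol excludes participants with severe renal insufficiency (eGFR <30 ml/min/1.73 BSA". Section 2.1.1.7 requires serum creatinine ≤1.5 mg/dL or Cockcroft-Gault clearance ≥60 mL/min. The Précis makes the creatinine limit strict ("Serum creatinine < 1.5 mg/dL, or creatinine clearance" ≥60 mL/min). Neither Section 2.1.1 nor Section 2.1.2 mentions eGFR.

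**Dose unit.** Section 3.1.3 has three participants "treated with moxetumomab pasudotox-tdfk 40 mg/kg and rituximab", and Section 10.2 says "the next 3 participants will be treated with moxetumomab pasudotox-tdfk 40 mg/kg and rituximab". The table in Section 3.1.3.1 gives Level 2 as 40 mcg/kg, as do the other mentions of that level.

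**The concern.** The Précis and Section 3.2.1 give oral hydration as a measure against renal toxicity and hypovolemia. The protocol also treats excess fluid as a hazard: Section 3.2.1 monitors weight gain for capillary leak syndrome and asks for chest imaging when fluid overload raises weight by more than 10%. Conflicting volumes therefore matter in both directions.

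Both sets of instructions are in use. Section 3.2.1 refers staff to Appendix C for administration and preparation, and to Section 3.2.3 for pre-infusion hydration. A person caring for a 48-kg participant finds two different instructions and nothing that says which governs.

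The other two items are of lower rank. The gadolinium risk statement relies on a safeguard that the eligibility criteria do not state, and the dose-escalation text carries a wrong-looking unit in two places.

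**Working it through.** **1. Glass count.** Inputs: 6 L with twelve 8-oz glasses, and 2 L with eight 8-oz glasses (both Appendix C, Step 8); 24 cups (legible part of the Appendix D diary). The documents give no ounce conversion. I assume the US fluid ounce, 29.57 mL, with the imperial ounce, 28.41 mL, as a variant, and a cup of 8 oz.

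Volume = glasses × 8 oz × mL per oz.

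- Stated 2 L: 8 × 8 × 29.57 mL = 1.89 L. This reproduces, after rounding.
- Stated 6 L: 12 × 8 × 29.57 mL = 2.84 L. This does not reproduce; 2.84/6 = 47%, and 6/2.84 = 2.1.
- Imperial variant: 12 × 8 × 28.41 mL = 2.73 L.
- Appendix C's own ratio: 12 × (2 L/8) = 3.0 L.
- Diary: 24 × 8 × 29.57 mL = 5.68 L, close to 6 L. One cup an hour for 24 hours gives the same.

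No variant turns twelve 8-oz glasses into 6 L.

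**2. Participants under 50 kg.**

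| Source | Oral, per day | IV before / after | Weight rule |
|---|---|---|---|
| Précis; Section 3.2.1 | about 6 L | no volume given | none |
| Section 3.2.3 scheme | 6 L | 1 L / 1 L | none |
| Appendix C, general | up to 6 L | 1 L / 1 L | – |
| Appendix C, under 50 kg | up to 2 L | 0.5 L / 0.5 L | under 50 kg |

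Dosing-day totals under 50 kg:

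- Section 3.2.3: 6 + 1 + 1 = 8 L.
- Appendix C: at most 2 + 0.5 + 0.5 = 3 L.

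**3. Renal exclusion.** Section 2.1.1.7 is an either/or rule, so a participant who meets the creatinine limb qualifies on renal function whatever the clearance. An illustration with the protocol's formula, clearance = (140 − age) × weight/(72 × creatinine), uses age 84 (the oldest patient in the phase 3 trial described in Section 1.2.1) and an assumed weight of 50 kg:

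- Creatinine 1.5: 56 × 50/(72 × 1.5) = 25.9 mL/min. This meets Section 2.1.1.7 but not the strict creatinine limit in the Précis.
- Creatinine 1.4: 56 × 50/(72 × 1.4) = 27.8 mL/min. This meets both.

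These values are not eGFR per 1.73 m². Scaling 25.9 by 1.73/BSA, for assumed body surface areas of 1.45, 1.50 and 1.55 m², gives 30.9, 29.9 and 28.9, which straddles 30. The example shows only that the rule sets no floor on clearance.

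**4. Dose unit.** At an assumed 70 kg, 40 mcg/kg is 2.8 mg, or three of the 1-mg vials in Appendix C. At 40 mg/kg it is 2,800 mg, or 2,800 vials. The second is not a plausible preparation, so the two entries read as unit slips.

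**The case against.** **On hydration.** The Précis, Section 3.2.1, the Section 3.2.3 scheme and the legible diary text all fit 6 L, so the glass-count error is confined to one parenthesis. The wording is partly advisory, and the under-50-kg text can be read as a specific exception to a general instruction; the 8 L to 3 L comparison sets a general target against a subgroup ceiling. Much of this stands. It does not remove the conflict: the exception appears only in Appendix C, while Section 3.2.1 sends pre-infusion hydration to a scheme without it. Agreement among several places also does not settle which figure was intended.

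**On the diary.** A reader might infer that the diary is wrong. The documents do not support that: its instructions are badly garbled in the text available, and the legible 24 cups fits 6 L. Whether it carries an under-50-kg instruction cannot be established.

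**On the safety endpoint.** A reader might infer that HUS and renal events decide it. They do not. Section 3.1.2 counts all treatment-related grade 3 or higher events with listed exceptions, and one exception covers grade 3 HUS that resolves within 2 weeks without significant complications. Section 10.4.2 requires no more than 2 DLTs in 10 participants. HUS and renal events can contribute to that count. Nor is fluid the only renal measure: Section 3.2.1 pairs it with aspirin.

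**On divergence between sites.** The documents describe care and dispensing at the NIH Clinical Center. Different practice across sites is not shown; the conflict is between pages of one protocol.

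**On the dose unit.** A reader might take the 1000-fold difference as a live overdose risk. Section 3.1.3 is a past-tense account, the Section 10.2 text is labelled as the initial determination, and Section 3.1.4 records that escalation had reached 40 mcg/kg without DLT. The entries need correcting but carry little operational weight.

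**On renal function.** A reader might take 25.9 mL/min as proof that patients with eGFR below 30 qualify. It is unindexed and rests on an assumed weight, and such patients would be uncommon under Section 2.1.1.7. What stands is that the stated exclusion is not written as a criterion.

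**Conclusion.** The concern holds, with hydration as the main point. The 6 L and twelve-glass figures in Appendix C differ by a factor of about 2.1 (2.0 by the appendix's own ratio). Under 50 kg, the two hydration schedules differ by at least 5 L on a dosing day if each is taken at its stated volume. The glass-count result depends only on the ounce conversion, and neither ounce rescues it; the under-50-kg conflict needs no assumption beyond reading the sections together.

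The eGFR mismatch is secondary: a safeguard is described in Section 12.4.4.8 and is absent from Sections 2.1.1 and 2.1.2, and the creatinine-or-clearance rule does not guarantee it. The two mg/kg entries are minor.

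The statistical analysis is unaffected. This is a matter of consistent instructions for participant care.

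**What to change.** - Reconcile the Précis (Administration), Sections 3.2.1 and 3.2.3, and Appendix C Steps 6 and 8, so that litres, glass counts and the under-50-kg instructions agree. The sponsor decides which values apply; none is proposed here.
- Check the Appendix D diary against the reconciled text, and reissue it only if it differs.
- Correct the cross-reference in Section 4, which sends readers to Section 3.1.4 for renal prophylaxis; that section is Dose Expansion and contains none.
- Reconcile Section 12.4.4.8 with Section 2.1.1.7 and the Précis eligibility text, so that the claimed exclusion either appears as a criterion or is no longer claimed. Settle the ≤1.5 versus <1.5 creatinine wording at the same time.
- Reconcile the dose unit in Sections 3.1.3 and 10.2 with the Section 3.1.3.1 table.

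The cost is one wording amendment with its usual IRB review. Because Appendix C carries a note of FDA approval, its Step 8 text should be checked against that source when it is edited.
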